The findings of this study will inform clinicians and investigators whether use of mobile seat interface pressure mapping as a compensatory-based intervention has a positive impact on trunk movement and self-efficacy for completing weight shifts in wheelchair users who lack sensation. Another contribution of this work is an exploration of the relationship between self-efficacy and movement in wheelchair users.

Primary Aim. Trunk movement in seated wheelchair users with SCI will increase when the user has access to a mobile seat interface pressure mapping system to self-monitor pressure distribution on their wheelchair seat cushion.

Secondary Aim. Self-efficacy for use of weight shifts as a pressure ulcer prevention strategy in wheelchair users with SCI will increase through structured education and with access to the mobile seat interface pressure mapping system to self-monitor pressure distribution on their wheelchair seat cushion.

Hypotheses:

Hypothesis 1. Weight shifts (counts of forward and side leans) will be higher with access to the mobile seat interface pressure mapping system than without it.

Hypothesis 2. Overall trunk movement (counts of vector magnitude) will be higher with access to the mobile seat interface pressure mapping system than without it.

Hypothesis 3. Self-efficacy rating immediately after education for weight shifts will be higher than self-efficacy rating taken prior to education.

Hypothesis 4. Self-efficacy rating during access to mobile seat interface pressure mapping at home will be higher than rating after education for weight shifts and higher than rating during phases when there is no access to the pressure mapping system.

Background (Include relevant experience, gaps in current knowledge, preliminary data, etc.):

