This research study addresses pressure ulcer prevention through introduction of a novel compensatory approach to improve weight shifting movements and self-efficacy in achieving the goal of preventing pressure ulcers. It is proposed that use of an on-demand, real-time, visual display of seat interface pressure ([name], 2013; [name], Rindflesch, & [name], 2013) will provide key feedback that allows wheelchair users with poor or absent sensation to immediately see the results of weight shifting and thus feel more confident in their ability to manage the build-up of pressure by using weight shifts effectively. Use of seat interface pressure mapping throughout one's typical daily routine has the potential to impact self-efficacy for managing skin health and also to improve weight shift adherence over time. This purpose of this study is to explore the potential benefit

of seat interface pressure mapping as a compensatory intervention strategy for impaired sensation in spinal cord injured wheelchair users.

Study Design and Methods

Methods: *Describe, in detail, the research activities that will be conducted under this protocol:*

This is a longitudinal, within-subject, repeated (A-B-A-B) measures design. Two interventions will be provided: structured education regarding pressure ulcer prevention through weight shifts at start of study and use of a mobile seat interface pressure map (IPM). Outcome measures include self-efficacy (SE) for weight shift movements and a measure for trunk movements. Figure 1 provides an overview of the design and sequence of measurements.

[figure not shown]

Figure 1. Details of study design.

Independent variables (IV). There are two independent variables in this study.

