- 1. Access to the mobile seat interface pressure mapping system (IPM) as a visual feedback system.** This mobile IPM system was designed to provide visual information about seat interface pressure distribution to compensate for lack of sensation on the sitting surface. This variable will be toggled on and off between the A and B phases of the study. The participants will have access to the visual feedback while learning how to complete weight shift maneuvers at the initial visit and then again at home during the A phases (weeks 2 and 4). During the B phases (weeks 1 and 3), they will not have access to the visual feedback from the pressure map. The pressure mapping system consists of a commercially available pressure mat by Vista Medical, and a mobile web-application developed by the research team through a CoDE award provided by the Center for Innovation in 2012 to display the pressure map information on a smartphone screen. The pressure mat connects to the smartphone via Wifi. The smartphone accesses the web application via the phone's data plan while connected to

the mat to display the pressure readings to the user on the phone. No information about the individual, except for the research participant ID number is transmitted to the web application. Each research participant will have a unique password associated with their own ID to use when they log into the web application. The web application resides on a Mayo Clinic server.

2. Education about pressure ulcer risk and how to perform weight shift movements.

Structured education for performance weight shift maneuvers and pressure ulcer prevention will occur during the initial visit. The education method used aligns with principles of the social cognitive theory to facilitate learning. The purpose in providing the education is to ensure all of the participants receive uniform instruction in how to perform weight shifts and to facilitate understanding of the importance of completing them as a protective measure against pressure ulcer development. Because each participant will come into the study at varying levels of understanding about pressure ulcer risk and knowledge of how to complete weight shift maneuvers, the education component is critical to ensure all participants are provided with the same information in the same way.

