2. **Self-efficacy for performing weight shifts.** The second dependent variable, self-efficacy, is measured with a series of four individual questions about self-efficacy for weight shifts for pressure ulcer prevention (Appendix A). Each question is answered by choosing a number from 0-100 to indicate confidence level. This assessment includes an initial question that targets an individual's outcome belief about whether they believe that completing weight shifts will prevent pressure ulcers. This is followed by three questions about their own judgement of their immediate capability to complete weight shift maneuvers based on three criteria: effectiveness (moving enough to impact pressure distribution), consistency (completing weight shifts every half hour), and duration (holding weight shifts for two minutes). The items were written following principles outlined in Albert Bandura's guide to developing self-efficacy assessments (A. Bandura, 2006).

The score for each of the four items will allow preliminary analysis of any change in self-efficacy for specific components of performing weight shifts with the outcome of pressure ulcer prevention. The self-efficacy questions (SE) will be administered in person or by phone a total of 7 times: at start of initial session before any education, at end of session when education is completed, on day 2 when participant has been home for 1 day but no other intervention has been provided (test-retest), and at the end of each of the four phases. The self-efficacy survey will be given twice during the initial visit, 4 times over the phone when participant is called each week, and 1 time during the last visit for a total of 7 times.

Additional demographic information will be obtained from existing medical records and will include date of onset of spinal cord injury, date of birth, history of pressure ulcers on sitting surface, history of pressure ulcer repair surgery, level of spinal cord injury and severity of injury.

Resources: *Describe the available resources to conduct the research (personnel, time, facilities, mentor commitment, etc.):*

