Weight shifts will be counted as described earlier based on offset angles. The average number of weight shifts for each type of weight shift will be documented by phases A1, B2, A2, B2. The analyses to test the primary hypothesis that overall trunk movement (vector magnitude) and weight shifts will increase in frequency with the use of the mobile pressuring mapping system will be tested using Linear Mixed Effects Regression. When appropriate, post-hoc tests will be performed to test main effects. If a phase x session interaction is present, post hoc tests to analyze and interpret the interaction will be used. Significance is set at $\alpha=0.05$.

Self-efficacy scores will be analyzed by comparing scores SE #1 vs #2, #2 vs #3 (test-retest), and #4 vs #5 vs #6 vs #7 to determine effect of education and use of mobile IPM on self-efficacy. The analyses to test the secondary hypothesis that the scores for the self-efficacy items will increase after education and will increase again with the use of the mobile pressuring mapping system will be tested using Linear Mixed Effects Regression. When appropriate, post-hoc tests will be performed to test main effects. If a phase x session interaction is present, post hoc tests to analyze and interpret the interaction will be used. Significance is set at $\alpha=0.05$.

The results will help determine if there is a cause/effect relationship between use of the pressure map and any increase in weight shifts if that is detected and if results are significant, we can conclude that use of the map resulted in increased movement. We can't conclude that there will be a reduction in

pressure ulcers but we can say that weight shifts, a factor known to contribute to reduced pressure ulcer risk, increases when a wheelchair user has access to a compensatory assistive device to accommodate reduced sensation. The same is true for results of the self-efficacy assessments. We would expect the mean score to improve at each subsequent time-point.

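### The expected rise in self-efficacy at every rating contradicts Hypothesis 4 when the map is withdrawn, and with no contrast or time term named, a plain upward trend could be credited to the map

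*Combined protocol and SAP*

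**What the plan says.** The Methods section describes the study thus: "This is a longitudinal, within-subject, repeated (A-B-A-B) measures design". Independent variables, item 1, places home access to the map in weeks 2 and 4 and adds: "During the B phases (weeks 1 and 3), they will not have access to the visual feedback from the pressure map".

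Dependent variables, item 2, schedules seven self-efficacy ratings. #1 comes before education and #2 after it. #3 is on day 2, when "no other intervention has been provided (test-retest), and at the end of each of the four phases", the last of which are #4 to #7.

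Hypothesis 4 predicts this for the rating with home access: "higher than rating after education for weight shifts and higher than rating during phases when there is no access to the pressure mapping system".

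The Data Analysis Plan compares #1 with #2, #2 with #3 (again labelled test-retest), and #4, #5, #6 and #7 with one another, by linear mixed effects regression at alpha 0.05. For the last set it gives no direction, contrast or decision rule. Post-hoc tests are left to judgement. The closing paragraph attributes a significant increase in movement to the map, says the same holds for the self-efficacy results, and ends: "We would expect the mean score to improve at each subsequent time-point".

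**The concern.** The plan makes opposite predictions at the step from #5 to #6, the only point in the rating series where home access is withdrawn. In a within-subject reversal design, that step does most to separate an effect of access from a general rise over time. Learning, repeated asking or a lasting effect of the education session would all produce steady improvement without any contribution from the map.

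The step from #2 to #3 has a related conflict. If nothing intervenes and the pair is meant to show repeatability, a rise there signals drift in the instrument or the respondent and should not be the expected result.

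What is at stake is the interpretation of the secondary aim. The analysis section names no contrast that would tell a map effect from a trend, and its one stated pattern over time is the pattern a trend would give.

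**Working it through.** The documents give no power, effect size or SD for self-efficacy, so there is no planned figure to reproduce. The count of ratings does reproduce: 1 + 1 + 1 + 4 = 7 by timing, and 2 + 4 + 1 = 7 by mode of administration.

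**1. Mapping.** From the schedule: #4 = end of week 1 (no map), #5 = end of week 2 (map), #6 = end of week 3 (no map), #7 = end of week 4 (map).

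**2. Predictions side by side.**

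| Comparison | Hypothesis 4, phase by phase | Closing sentence |
|---|---|---|
| #5 and #7 vs #2 | higher | higher |
| #5 vs #4 | higher | higher |
| #7 vs #4 | higher | higher |
| #7 vs #6 | higher | higher |
| #6 vs #5 | **lower** | **higher** |

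Hypothesis 4 says nothing about #2 vs #3. The closing sentence implies a rise there, against the test-retest label. A strictly rising series meets three of the four map/no-map pairs and fails one. It can never meet all four, because it forces #6 above #5.

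**3. Pooled contrast under a pure trend.** Let the rise be d per rating, with no map effect, so #4 to #7 are 0, d, 2d, 3d.

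- Mean(#5, #7) − mean(#4, #6) = (d + 3d)/2 − (0 + 2d)/2 = 2d − d = **+d**.
- The plan mentions a phase-by-session interaction without defining session. If session means first or second cycle, the map effect is the average of (#5 − #4) and (#7 − #6), which is still d. The interaction is d − d = 0, so it gives no warning.

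**4. Chance of a significant result from trend alone (illustration).** Assumptions: n = 30 (target accrual), independent within-person errors with SD s, two-sided 0.05, normal approximation. The contrast has variance 4 × (1/4) × s²/n, so its standard error is s/√30. The chance of a significant positive result is Φ(d/SE − 1.96).

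- s = 10, d = 5: SE = 1.826, and Φ(2.739 − 1.96) = 78%.
- s = 20, d = 5: SE = 3.651, and Φ(1.369 − 1.96) = 28%.
- Over s = 20 to 10: 8% to 19% for d = 2, and 59% to 99% for d = 8. With no drift it is 2.5%.

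Both d and s are assumed; the documents give neither.

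**5. Effect of a linear time term.** Code map as m = (−½, ½, −½, ½) and time as t = (−1.5, −0.5, 0.5, 1.5).

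- Σmt = 0.75 − 0.25 − 0.25 + 0.75 = 1, Σm² = 1, Σt² = 5. So R² = 1²/(1 × 5) = 0.2.
- Variance inflation = 1/(1 − 0.2) = 1.25, and √1.25 = 1.118, so the standard error is about 12% wider.
- The adjusted contrast is 0.75(#5 − #6) + 0.25(#7 − #4). Under the linear rise it is −0.75d + 0.75d = **0**.
- It is not zero for every rise. For a one-step gain that then persists (0, 1, 1, 1), the pooled contrast is 0.5 and the adjusted one is 0.25. The withdrawal step therefore still has to be reported by itself.

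**6. Phase labels.** Item 1 calls the map weeks A (weeks 2 and 4), while the phases are listed elsewhere as A1, B1, A2, B2. If that listing were chronological with A as access, the map would be on in weeks 1 and 3. A steady rise would then fail three of the four pairs, and the pooled contrast would be −d. The conflict with Hypothesis 4 remains under either reading.

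**The case against.** The disputed sentence is an expectation, not a test. The analysis is specified in the preceding paragraph, and removing the sentence would alter no model. The planned comparison of #4 to #7 could itself show #6 above #5. The sentence may loosely mean the two steps in the restated secondary hypothesis: a rise after education and a further rise with the map. The extension of the causal reading to self-efficacy is also brief, and it follows a passage that partly limits the claim. Finally, Hypothesis 4 can be read as map phases against no-map phases on average, and a steady rise does not refute that reading.

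Most of this stands, and it limits the point. A reader might infer that a steady rise refutes half of the map hypothesis, or that the plan declares such a rise a success. The documents support neither. One of four map/no-map pairs fails, the comparison with the post-education rating is met, and no success criterion is written down.

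The objection does not remove the contradiction under the phase-by-phase reading, or the conflict with the test-retest pair. The averaged reading makes the other weakness more important, because the averaged contrast is the one that a trend alone makes positive.

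**Conclusion.** The point holds in a limited form. The closing sentence cannot be true together with Hypothesis 4 read phase by phase, and it does not fit the use of #2 vs #3 as test-retest. No other section reconciles them.

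This goes beyond wording because no contrast or time term is named for #4 to #7 and no-map always comes before map. A linear rise with no map effect then yields a pooled difference of one full step, which the plan as written could credit to the map. That one-step figure is exact for a linear rise with access in weeks 2 and 4. The 28% to 78% range depends on the assumed drift, SD and independent errors, and only illustrates scale. The matter concerns the secondary aim of a 30-person study and needs no new data to correct.

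**What to change.** - Replace the closing sentence with the pattern Hypothesis 4 implies: #5 and #7 above #2, #4 and #6. State separately that no change is expected from #2 to #3.
- In the mixed model for #4 to #7, prespecify the map vs no-map contrast with a linear time term.
- Add the comparison of #2 with #5 and #7, which Hypothesis 4 requires and the listed comparisons omit.
- Report #5 minus #6 with its confidence interval as the withdrawal comparison.
- State that a rise at every rating will be reported as improvement over the study that cannot be separated from learning or carry-over, and not by itself as a map effect.
- Reconcile the A and B labels with the order of the weeks.

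A rule asking only that the three steps have the right signs would not be enough. With no effect and exchangeable means, #4 < #5 > #6 < #7 arises in 5 of 24 orderings, about 21%, and such a rule leaves out #2.

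The changes are to text and model specification, with no added visits or participants. The time term widens the standard error of the map contrast by about 12%, assuming independent, equal-variance within-person errors. A lasting gain in confidence would count for less as evidence for the map. If the sponsor does expect lasting gains, Hypothesis 4 is the text to revise, and the plan should say how such gains will be interpreted.
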